		
• Remove IPCW analysis as a supportive analysis per team discussion.• Clarify how multivariate Cox regression will be done.• Clarify how the analysis using CRF based stratification factors will be done.
		Section 3.8.2, 
• Remove central assessed PFS as a secondary end point per protocol amendment.• Remove misplaced PK objective.
		Section 3.8.2.1: 
• Update the interim analysis for OS per protocol amendment.• Simplify the subgroup analysis by making a reference to the subgroup analysis section.• Clarify that the OS analysis will be done only after the primary analysis is statistically significant.• Clarify how the multivariate Cox regression should be done.
		Section 3.8.2.2: remove BIRC PFS section which has been replaced by Audit-based BIRC assessment of PFS in section 3.8.1.5.
		Section 3.8.2.5: Clarify censoring rule for DOR.
		Section 3.8.2.6: ECOG PS 
• Update the rule when 2 ECOG assessments fall in the same window to align with ML2 submission.• Clarify the definition of definitive deterioration.• Add estimation of HR to align with ML2 submission.
		Section 3.8.2.7: 
• Update the mixed model to align with ML2 submission.• Add EOT and efficacy FU to table 3-5.• Add linear model for selected time points.• Clarify time is a continuous variable in mixed model.
		Section 3.9.1.4: Add number of occurrences output per safety guidance.
		Section 3.9.1.5: Update CNAE to AESI per new SAP template.
		Section 3.9.2: 
• Add definition of Total ANC.• Update analysis for LFT to align with ML2 submission and add clarification.• Add analysis for time to onset and duration of AE to align with ML2 submission.• Add box plot.• Clarify that CTCAE calculation is based on observed data only.
		Section 3.9.4: 
• Add language to clarify how unscheduled assessment is summarized.• Remove parameter RR to align with the notable ECG table.• Update notable heart rate criteria to align with new SAP

Version	Date	Changes

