As the main analysis and to best utilize the repeated PRO assessments, a repeated measures model for longitudinal data will be used to compare the two treatment arms in sub-scales obtained from EORTC QLQ-C30 and the VAS score of EQ-5D-5L over time. This longitudinal model will include terms for treatment, the randomization stratification factors, time (duration in weeks counting from the time of baseline measurement to the time of a particular post baseline measurement), baseline value as main effects, and an interaction term for treatment by time. Time will be considered as a continuous variable in this analysis. As a first approach, an unstructured correlation matrix will be used to model the correlation within patients. The structure of the correlation matrix will be investigated and simplified using likelihood ratio tests if appropriate. Time is considered as a continuous variable in the analysis. The data for selected time points will be fitted using a linear model using treatment, stratification factors, baseline value as covariates. The differences in least square means between the experimental and control group, and the corresponding 2-sided 95% CI at selected time points will be presented.

For the mixed effects model, patients with baseline and at least one non-missing post-baseline assessments will be included. This analysis will only include assessments up to the time point where there are at least 50 patients on each of the treatments. Data collected up to EOT assessment will be included.

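### Selected-visit PRO differences appear to rest on separate complete-case linear models, and the main mixed model allows only a straight-line treatment effect; one visit-based mixed model would serve better

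*SAP*

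**What the plan says.** The SAP file holds a plan for the final study report and a plan for the primary PFS analysis. The PRO methods are in Section 3.8.2.7 of the latter.

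- **Main analysis.** A repeated measures model is introduced with "As the main analysis and to best utilize the repeated PRO assessments". Its terms are treatment, the randomization strata, time in weeks, "baseline value as main effects, and an interaction term for treatment by time". On the form of time: "Time will be considered as a continuous variable in this analysis", repeated a few lines later. As a first approach "an unstructured correlation matrix will be used to model the correlation within patients", with simplification allowed. It takes patients with a baseline and at least one later score, up to the end-of-treatment (EOT) assessment and while each arm has at least 50 patients.
- **Selected visits.** Directly afterwards: "The data for selected time points will be fitted using a linear model using treatment, stratification factors, baseline value as covariates". The next sentence presents "The differences in least square means between the experimental and control group", with two-sided 95% confidence intervals, at selected time points. The visits are not named.
- **Document history.** The Amendment 1 entry for this section lists "Add linear model for selected time points" as an item separate from the mixed-model update.
- **Protocol.** Section 10.5.5 rules out imputation of missing assessments and plans no formal PRO tests. Table 3-1 lists change from baseline in QLQ-C30 global health status as a secondary endpoint.

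**The concern.** The selected-visit model has no time term and no within-patient correlation. With no imputation, each fit can use only patients who have a score at that visit. It adjusts for baseline but not for the scores in between, which are the ones most likely to predict who leaves. If patients with worse recent scores leave sooner, and the arms lose patients at different rates, the two groups compared at a late visit are selected to different degrees.

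Differential loss is built into the planning assumptions. PRO collection stops at progression (Protocol Table 7-9), and the assumed median PFS is 9 months on control and 13.4 months on ribociclib.

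The main model has a different limit. With one time slope and one treatment-by-time term, the arm difference at week t is b1 + b3·t. That gives a value at every visit, but only on a line. An early toxicity-related dip that resolves, or a late benefit, would be smeared across all visits.

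**Working it through.** The plan gives no PRO precision or power figure, so there is nothing to reproduce. The PRO standard deviation, correlation and dropout mechanism are also not given and are assumed below.

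**1. Expected loss, from Protocol Section 10.8.** Exponential PFS, S(t) = 0.5^(t/median); 660 patients at 2:1 (440/220); 19 months' uniform accrual; cut-off at month 26.
- Week 24: 75% versus 65% event-free (331 versus 144 patients).
- Week 48 (11.04 months): 0.5^(11.04/13.4) = 56% versus 0.5^(11.04/9) = 43%. The share followed that long is (26 − 11.04)/19 = 0.79, leaving about 196 versus 74.
- Week 72: 42% versus 28%, about 93 versus 30 with the same allowance.

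Per 8-week interval (1.84 months) the hazards are ln2/9 × 1.84 = 0.142 and ln2/13.4 × 1.84 = 0.095. As probabilities: 1 − e^(−0.142) = 13.2% on control and 1 − e^(−0.095) = 9.1% on ribociclib.

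**2. Bias with no true difference (simulation).** Negative values are against ribociclib. Dropout depends on the last observed score, so it is missing at random.

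Setting A: six visits to week 48, SD 20, constant correlation 0.6, dropout 13.2% versus 9.1% per visit.

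| Odds of dropout per 10 points lower | Per-visit model, week 48 | Visit-based mixed model | SAP linear-time mixed model |
|---|---|---|---|
| ×1.3 | −0.45 to −0.54 | about 0 | about 0 |
| ×2.0 | −0.76 to −0.98 | about 0 | about 0 |

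The per-visit ranges come from two runs. The spread at ×2.0 is mostly whether the rates apply to a patient with an average score or are held as the average over patients remaining; the rest is simulation error.

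Setting B: nine visits to week 72, correlation 0.4 + 0.6 × 0.7^lag, dropout about 13% versus 9%. Log-odds of dropout rise by 0, 0.5 or 1.0 per SD of lower score (odds ×1, ×1.28 or ×1.65 per 10 points, since e^0.25 = 1.28 and e^0.5 = 1.65).

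| Log-odds slope | Per-visit, week 48 / 72 | Visit-based, week 48 / 72 | Linear-time, week 48 / 72 |
|---|---|---|---|
| 0 | 0.14 / 0.06 | 0.14 / 0.06 | 0.05 / 0.08 |
| 0.5 | −0.49 / −0.86 | 0.12 / 0.03 | 0.25 / 0.40 |
| 1.0 | −0.88 / −1.35 | 0.09 / −0.01 | 0.37 / 0.59 |

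Monte Carlo error is about 0.1 point. The per-visit model is unbiased when dropout is unrelated to score. The linear-time model drifts slightly here because it has a single baseline slope, while the correlation with baseline decays over visits. That is a reason for a baseline-by-visit term.

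**3. Curved effect, dropout unrelated to score.** Suppose the true difference is −5 at week 8, −2.5 at week 16 and 0 from week 24.
- Setting A: the straight line reads about −1.8 at week 24 and +1.2 at week 48.
- Setting B: it reads −3.07 at week 24 and +1.36 at week 72; the visit-based model gives −0.02 and 0.06.

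**4. Scale.** The residual SD after baseline adjustment is 20 × √(1 − 0.6²) = 16. With dropout alone, week-48 numbers are 440 × 0.909^5 = 273 and 220 × 0.868^5 = 108, so SE = 16 × √(1/273 + 1/108) = 1.82. With the step 1 counts, SE = 16 × √(1/196 + 1/74) = 2.18. The setting A bias is therefore between 0.45/2.18 = 0.21 and 0.98/1.82 = 0.54 of a standard error.

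**The case against.** The strongest reply is that the plan's main PRO analysis is already a likelihood-based mixed model using every patient with a baseline and one later score. In setting A it is as unbiased as the proposed model. This stands: a reader might infer that the plan has no dropout-robust PRO analysis, and the SAP text contradicts that. A reader might also infer that the main model cannot give a difference at a visit. It can, through b1 + b3·t; the fault is only the straight line, and it bites only if the effect is curved. The 5-point dip is an illustration, not a figure from the documents.

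Second, the SAP does not say outright which model supplies the least-squares mean differences. The sentence order, the covariate list and the separate document-history entry point to the per-visit models, but this is an inference.

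Third, the effect is small, and in these scenarios it runs against ribociclib, so it would not create a false quality-of-life benefit. The protocol plans no formal PRO tests.

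Fourth, continuous time was a deliberate choice, recorded in the document history, and it takes off-schedule EOT scores at their actual week. Table 3-5 gives EOT its own row, so a visit factor needs a mapping rule or it loses scores that are often the last before dropout. This is a real cost and belongs in the fix.

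Fifth, the primary analysis took place in January 2018, PRO collection stopped with protocol amendment 4, and the final-report SAP describes no PRO analysis. Any change now would be supportive.

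**Conclusion.** The point holds as a modest improvement. The selected-visit differences appear to come from complete-case fits that ignore intermediate scores. Under the assumed SD of 20, correlation of 0.6, dropout of about 13% versus 9% per visit and dropout odds of ×1.3 to ×2.0 per 10 points, they are off by roughly 0.5 to 1 point at week 48, about a fifth to a half of a standard error. If dropout is unrelated to earlier scores there is no bias. The main mixed model handles missing-at-random dropout when its mean structure is right, but it forces the arm difference onto a line.

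The sizes depend on inputs the documents do not give; the mechanisms follow from the model forms. A visit-based model does not cure dropout either: progression or death may break missing at random. No sample size, alpha or primary conclusion is affected.

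**What to change.** In Section 3.8.2.7, replace the per-visit linear models with one mixed model and take the selected-visit differences and 95% confidence intervals from it. Specify:

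- visit as a factor, using the Table 3-5 windows;
- treatment-by-visit and baseline-by-visit terms, and the randomization strata;
- unstructured covariance, which needs discrete visits anyway, with a named fallback if it does not converge;
- the selected visits by name, within the existing limit of 50 patients per arm;
- how EOT scores map to visits.

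The continuous-time model may stay as the overall summary over time. State that validity rests on missing at random, and add a sensitivity analysis for departures from it.

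The cost is SAP wording, more parameters, a possible covariance fallback and the EOT rule. No new data are needed. For the results already produced, label it a supportive re-analysis.

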**Table 3-1 Objectives and related endpoints**

Objective	Endpoint	Analysis

Primary
 
To compare PFS between ribociclib in combination with fulvestrant to placebo in combination with fulvestrant among men and postmenopausal women with HR+, HER2-negative advanced breast cancer who received no or only one prior endocrine treatment for advanced disease
	
The primary end point is PFS based on local radiology assessments and using RECIST 1.1 criteria
	
Refer to Section 10.4

Secondary
 
To compare the two treatment arms with respect to overall survival.
 
To evaluate the two treatment arms with respect to overall response rate, clinical benefit rate, time to response and duration of response.
 
To evaluate the two treatment arms with respect to time to deterioration of ECOG performance status.
 
To evaluate the safety and tolerability of ribociclib in combination with fulvestrant.
 
To evaluate patient reported outcomes for health-related quality of life in the two treatment arms.
 
To characterize the pharmacokinetics (PK) of ribociclib (and relevant metabolites such as LEQ803) when given in combination with fulvestrant.
	
Overall survival
 
ORR and as defined by RECIST 1.1. CBR, defined as percentage of patients with CR, PR or SD lasting 24 weeks or longer, TOR, DOR per RECIST 1.1
 
Time to definitive deterioration of ECOG performance status from baseline
 
Frequency/severity of AEs, laboratory abnormalities
 
Time to 10% deterioration in the global health status/QOL scale score of the EORTC QLQ-C30
 
Change from baseline in the global health status/QOL scale score of the EORTC QLQ-C30
 
Concentration by time point for ribociclib (and relevant metabolites such as LEQ803)
	
Refer to Section 10.5

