
[figure not shown]
[figure not shown]
In addition, a repeated measurement analysis model may be used to compare the two treatment groups with respect to changes in the domain scores (global health status/QoL scale score, physical functioning, emotional functioning and social functioning scale scores of the QLQ-C30 index score and overall health status of the EQ-5D-5L, longitudinally over time. [REDACTED]

[figure not shown]
Time to definitive 10% deterioration in the global health status/QoL, physical functioning, emotional functioning, social functioning will be assessed. The time to definitive 10% deterioration is defined as the time from the date of randomization to the date of event, which is defined as at least 10% relative to baseline worsening of the corresponding scale score or death due to any cause. If a patient has not had an event, time to deterioration will be censored at the date of the last adequate QoL evaluation. The distribution will be presented descriptively using Kaplan-Meier curves. Summary statistics from Kaplan-Meier distributions will be determined, including the median time to definitive 10% deterioration along with two-sided 95% confidence interval. Additionally, time to definitive deterioration with different cutoff definitions (e.g. 5%, 15%) may be specified in the RAP as deemed appropriate. A stratified Cox regression will be used to estimate the hazard ratio (HR), along with two-sided 95% confidence interval.

[REDACTED]

[REDACTED]

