**For the following questions please circle the number between 1 and 7 that best applies to you**

29. How would you rate your overall health during the past week?

1      2      3      4      5      6      7

Very poor

Excellent

[figure not shown]
30. How would you rate your overall quality of life during the past week?

1      2      3      4      5      6      7

Very poor

Excellent

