The global health status/global QoL scale score of the EORTC QLQ-C30 is identified as a primary PRO variable of interest. The physical functioning, emotional functioning and social functioning sub-scale scores of the EORTC QLQ-C30, the visual analog scale (VAS) of the EQ-5D-5L, and worst pain item (based on question 3), pain severity index, and pain interference indices of the BPI-SF are identified as secondary PRO variables of interest. High scores in the EORTC QLQ-C30 represent a higher response level. Thus a high score for a functional scale represents a high / healthy level of functioning; a high score for the global health status / QoL represents a high QoL, but a high score for a symptom scale / item represents a high level of symptomatology /problems. Higher scores in the EQ-5D-5L also correspond to better health states. A higher score in BPI-SF corresponds to more pain.

The number of patients completing PRO questionnaires and the number of patients missing/expected to have PRO assessments will be summarized by treatment arm for scheduled assessment time points (the number of ongoing patients will be used as

denominator). Furthermore, the amount and the pattern of missing data may be explored by treatment arm and over time using summary statistics. The following categories will be used to describe whether the questionnaire was completed at a specific time point:

- yes, fully completed
- yes, partly completed
- no.

Scoring of raw data and methods for handling missing items or missing assessments will be handled according to scoring manuals for each respective patient questionnaire (Fayers 2001; Oemar and Janssen 2013; Cleeland 2009).

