Analysis of the time to definitive 10% deterioration in the primary and the secondary PRO variables of interest will be performed. Definitive 10% deterioration is defined as a worsening in score by at least 10% compared to baseline, with no later improvement above this threshold observed during the treatment period, or death due to any cause. Time to deterioration is the number of days between the date of randomization and the date of the assessment at which deterioration is seen. If a patient has not had an event prior to analysis cut-off, start of new anti-neoplastic therapy, lost to follow-up, end of treatment or withdrawal of consent, the time to deterioration will be censored at the date of the last evaluation before the earliest of these times. Only assessments collected while the patient is on treatment and on or before the end of treatment visit will be included in the PRO time to deterioration analysis. If deterioration is observed after two or more missing assessments, time to deterioration will be censored at the date of the last assessment prior to the deterioration. The rules for calculating number of missing assessments are the same as those for tumor assessments (see details in Section 2.5.5). Time to 10% deterioration in the global health status/QOL scale, and secondary PRO scales of interest as listed above, will be compared between the two treatment arms using a

stratified log-rank test (strata based on IRT data) at 2 sided 5% level of significance. The survival distributions will be presented descriptively using Kaplan-Meier curves. Summary statistics from the Kaplan-Meier distributions will be determined, including the median time to 10% deterioration and the proportions of patients without 10% deterioration at 2 month intervals. Both point estimates and 95% CIs will be presented. A stratified Cox regression model will be used to estimate the hazard ratio (HR) of time to deterioration, along with 95% confidence interval. Sensitivity analysis of time to definitive deterioration with different cut-off definitions (e.g. 5%, 15%) may also be considered if the number of events per arm is judged sufficient to draw relevant conclusions.

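### The 10%-of-baseline deterioration rule has no defined value on the BPI-SF pain scales for patients who start with no pain, and its QLQ-C30 version lacks a fixed-point sensitivity analysis

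*SAP*

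**What the plan says.** Protocol section 10.5.5 makes the threshold relative to the patient's own starting score: the event is one "which is defined as at least 10% relative to baseline worsening of the corresponding scale score or death due to any cause". It names four QLQ-C30 scales: "Time to definitive 10% deterioration in the global health status/QoL, physical functioning, emotional functioning, social functioning will be assessed". The secondary endpoint in Protocol Table 3-1 is "Time to 10% deterioration in the global health status/QOL scale score of the EORTC QLQ-C30".

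The SAP for the primary PFS analysis, section 3.8.2.7, keeps the relative threshold ("Definitive 10% deterioration is defined as a worsening in score by at least 10% compared to baseline, with no later improvement above this threshold") and widens the scope: "Analysis of the time to definitive 10% deterioration in the primary and the secondary PRO variables of interest will be performed". The secondary variables are listed in the same section. After the worst pain item the list continues: "pain severity index, and pain interference indices of the BPI-SF are identified as secondary PRO variables of interest". Each of these gets a stratified log-rank test at the two-sided 5% level and a stratified Cox hazard ratio. Death from any cause is also an event. Cut-offs such as 5% and 15% are optional sensitivity analyses and are relative too.

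Protocol section 7.2.6.3 scores BPI-SF items from 0 (no pain, or no interference) to 10. It builds the severity index as a sum of four items and the interference indices as item means. Neither document says what to do when the baseline score is 0.

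**The concern.** A percentage of baseline works only if the baseline is above zero. On a pain scale zero is an ordinary and favourable starting value, and those are the patients in whom new pain would be most noticeable. If their event status depends on how a programmer wrote the comparison, so do the pain survival curves, the test and the hazard ratio.

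A second, smaller matter concerns the QLQ-C30. Its scales move in coarse steps, so a percentage threshold and its sensitivity cut-offs can reduce to the same rule. The optional analyses may then show less about robustness than they appear to.

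**Working it through.** The documents give no event count or power for the patient-reported endpoints, so there is no figure of the plan to reproduce.

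**Inputs.** Threshold 10% of own baseline (Protocol 10.5.5; SAP 3.8.2.7). BPI-SF items 0-10 (Protocol 7.2.6.3). QLQ-C30 scales 0-100 (Protocol 7.2.6.1). Global health/QoL items such as "How would you rate your overall quality of life during the past week" have seven categories, and functional items have four (Protocol Appendix 4). Number randomised 727 (Protocol, Amendment 3 rationale).

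**Assumption.** Scoring is equal-weight and linear to 0-100, with items 29-30 = global, 1-5 = physical, 21-24 = emotional and 26-27 = social. The documents refer scoring to the EORTC manual and do not spell out this mapping.

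**Step 1: BPI-SF at baseline 0.** Percentage worsening = 100 x (follow-up - baseline) / baseline. For a lasting move from 0 to 6 this is 100 x 6/0, which is undefined. Two reasonable codings diverge:

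- Event if the score has risen and the rise is at least 0.10 x baseline. At baseline 0 the threshold is 0, so any rise is an event.
- Event if the percentage change is at least 10. At baseline 0 the value is missing, so no rise can be an event and only death can.

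On the worst pain item at baselines 1 to 9, a one-point rise is between 1/9 = 11.1% and 1/1 = 100%, so it always qualifies and the codings agree. At baseline 10 no rise is possible. The disagreement on that item is therefore confined to baseline 0.

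**Step 2: how many patients.** The share with baseline 0 is not in the documents. If it is p, about 727 x p patients are affected; each 10% is 0.10 x 727 = about 73.

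**Step 3: QLQ-C30 steps.** Steps = items x (categories - 1), and step size = 100 / steps. Global: 2 x 6 = 12, 8.33 points. Emotional: 4 x 3 = 12, 8.33. Physical: 5 x 3 = 15, 6.67. Social: 2 x 3 = 6, 16.67. The table counts non-zero baseline levels.

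| Scale | Levels | One step enough at 5% | at 10% | at 15% | 5% same rule as 10% | 15% differs from 10% |
|---|---|---|---|---|---|---|
| Global | 12 | 12 | 10 | 6 | 10 | 4 |
| Emotional | 12 | 12 | 10 | 6 | 10 | 4 |
| Physical | 15 | 15 | 10 | 6 | 10 | 6 |
| Social | 6 | 6 | 6 | 6 | 6 | 0 |

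On the global scale 8.33/83.33 = 10.0% meets the threshold and 8.33/91.67 = 9.1% does not. The required fall is therefore 8.33 points at ten levels and 16.67 points at 91.7 and 100.

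**Step 4: a fixed 10-point fall.** Global and emotional need two steps (16.67 points), physical two (13.33) and social one (16.67), at every baseline with room to fall that far. A patient at the lowest non-zero global level (8.33) has no such room.

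**The case against.** The reach is narrower than it first looks. The named secondary endpoint is global health/QoL, where a baseline of 0 leaves no room to worsen, so the division by zero does no harm there. The protocol lists no pain scale for this analysis, and the examples in SAP section 4.2 omit the BPI-SF. All this stands, but SAP section 3.8.2.7 does bring in the pain scales and tests them.

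A reader might infer that every pain-free patient would be counted as deteriorated at the first follow-up. The text does not support this: it requires a worsening, and an unchanged 0 is not one. Nor does it follow that such patients can never have an event, because death counts. The natural reading, any rise from 0, may be what the separate programming specifications contain; they are not available here.

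A reader might also infer that the sensitivity cut-offs cannot show robustness at all. That fails for 15%, which differs from 10% on three of the four QLQ-C30 scales.

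Other analyses do not use the 10% rule. The main one is a longitudinal model of the QLQ-C30 sub-scales and EQ-5D-5L visual analogue scale. For pain there are descriptive summaries, changes from baseline and worst-pain shift tables. The rule is the same in both double-blind arms, so no between-arm bias is shown. Protocol section 10.5.5 plans no formal testing of these data.

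Finally, it is late. The primary PFS analysis was in January 2018, questionnaire collection ended with Amendment 4, and the SAP for the final study report describes no patient-reported analysis. Any change is post hoc, which argues for keeping the QLQ-C30 definition and adding to it.

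**Conclusion.** The gap is real for the BPI-SF pain scales: as written, the SAP does not determine the pain-event status of a patient whose baseline is 0. The number affected cannot be stated from the documents. PFS, OS and the named global health/QoL endpoint are untouched by it.

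For the QLQ-C30 the point is one of sensitivity analysis. Under linear scoring the 5% cut-off repeats the 10% rule at 10 of 12 non-zero global levels and at every social level, and the required global fall doubles at the top two levels.

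Two stronger conclusions are tempting. One is that the relative rule fails to measure worsening on the QLQ-C30; but on the global scale the smallest qualifying fall is the same at ten of twelve levels, and choosing a relative or a fixed threshold is a trade-off. The other is that most patients deteriorate on a one-category change; the counts are of score levels, not patients, and no baseline distribution is given. The one-step result also does not carry over to finer scores such as the visual analogue scale or the multi-item pain severity index.

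**What to change.** **BPI-SF.** Replace the relative rule with a fixed rise of 10% of the scale range, and state that worsening is a rise. That is at least 1 point on the 0-10 worst pain item and the mean-scored interference indices, and at least 4 points on the severity index if it is scored as a 0-40 sum as in Protocol 7.2.6.3 (0.10 x 40 = 4). On worst pain this leaves the rule unchanged at baselines 1 to 9 and defines it at 0.

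**QLQ-C30.** Keep the pre-specified relative 10% definition and add a sensitivity analysis with a fixed fall of at least 10 points.

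**Cost.** SAP wording, a re-derivation from data already collected, and one extra table. BPI-SF results would not be directly comparable with any reported under the relative rule, and both changes should be labelled as made after the primary analysis.
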